15.2.1 All Adverse Events

Population: SAF analysis set

Adverse events will be summarized by worst severity (according to NCI-CTCAE version 4.03) per subject, using the most recent available MedDRA version (19.1 or later) PT as event category and primary SOC body term as Body System category.

Frequency tables for AEs captured on the “Adverse Events” eCRF pages will be based on TEAEs, i.e. those events with onset dates occurring within the treatment periods (as defined above).

A first overview table of adverse events will be provided by dose level and overall by summarizing the number and percentage of patients with any:

- TEAE
- TEAEs related to trial treatment, (i.e. M3814, RT, or Cisplatin)
- TEAEs related to M3814
- TEAEs related to RT
- TEAEs related to Cisplatin
- Serious TEAE
- Serious TEAE related to trial treatment, M3814, RT or Cisplatin
- TEAEs with grade ≥ 3
- TEAEs with grade ≥ 4
- TEAEs with grade ≥ 3 related to trial treatment, M3814, RT or Cisplatin
- TEAEs with grade ≥ 4 related to trial treatment, M3814, RT or Cisplatin

- TEAE leading to study discontinuation
- TEAE leading to death
- TEAE leading to death related to trial treatment, M3814, RT or Cisplatin

In addition, frequency tables summarizing events in the following categories will be prepared by dose level and overall, SOC and PT in alphabetical order:

- TEAEs
- TEAEs related to trial treatment (i.e., M3814, RT, or Cisplatin)
- TEAEs related to M3814
- TEAEs related to RT
- TEAEs related to Cisplatin
- Serious TEAEs
- Serious TEAEs related to trial treatment
- Serious TEAEs related to M3814
- Serious TEAEs related to RT
- Serious TEAEs related to Cisplatin
- TEAEs by worst CTCAE grade: any grade (including AEs with missing grade), grades ≥ 3 , ≥ 4 and 5
- TEAEs related to trial treatment by worst CTCAE grades: any grade (including AEs with missing grade), grades ≥ 3 , ≥ 4 and 5
- TEAEs related to M3814 by worst CTCAE grades: any grade (including AEs with missing grade), grades ≥ 3 , ≥ 4 and 5
- TEAEs related to RT by worst CTCAE grades: any grade (including AEs with missing grade), grades ≥ 3 , ≥ 4 and 5
- TEAE related to Cisplatin by worst CTCAE grades: any grade (including AEs with missing grade), grades ≥ 3 , ≥ 4 and 5
- TEAEs leading to death
- TEAEs related to trial treatment leading to death
- TEAEs related to M3814 leading to death
- TEAEs related to RT leading to death
- TEAEs related to Cisplatin leading to death

All tables will be sorted by alphabetical order of SOC and PT.

The listing for all AEs (whether treatment-emergent or not) will include all the data fields as collected on the “Adverse Events” eCRF pages with the following items:

- Formulation
- Dose level
- Subject identification number,
- First and last dose date
- Reported Term with SOC and PT
- Start and end date with their corresponding treatment day
- Treatment Emergent Adverse Events flag (N/Y)
- Timing related to treatment (if same day of treatment administration)
- TEAE related to M3814 flag (N/Y)
- TEAE related to RT flag (N/Y)
- TEAE related to Cisplatin flag (N/Y)
- Serious Adverse Events flag (N/Y)
- DLT flag (Y/N)
- CTCAE Grade
- Action taken M3814, with RT and with Cisplatin
- Outcome of AE
- AE occurred after COVID-19 pandemic start (Y/N).

CT.gov / EudraCT

Summary tables for non-serious adverse events excluding SAEs applying frequency threshold of 5% will be provided. The threshold will be applied on preferred term using overall column.

Evaluation of COVID-19 effects on AEs

The direct effect of COVID-19 for AEs will be assessed via listing of COVID-19 related AEs. The following listing will be generated using the ‘COVID-19 related terms MedDRA 23.0 update Spreadsheet’, considering all ‘search terms for COVID-19-related’ =’Y’. Same information as for the listing of all AEs will be provided.

15.2.2 Adverse Events Leading to Treatment Discontinuation

Population: SAF analysis set

An overview table of adverse events leading to discontinuation or dose reduction will be provided by dose level and overall by summarizing the number and percentage of patients with any:

- TEAE leading to temporary discontinuation of at least one trial treatment, all trial treatments, M3814 (regardless of other trial treatments status), RT (regardless of other trial treatments status), Cisplatin (regardless of other trial treatments status) (corresponding to AEs with action taken = “Drug interrupted” for MSC2490484A or Cisplatin respectively and “Dose skipped” for Radiotherapy)
- TEAE leading to permanent discontinuation of at least one trial treatment, all trial treatments, M3814 (regardless of other trial treatments status), RT (regardless of other trial treatments status), Cisplatin (regardless of other trial treatments status) (corresponding to AEs with action taken = “Drug withdrawn” for M3814, Radiotherapy or Cisplatin respectively)
- TEAE leading to dose time delayed of RT (corresponding to AEs with action taken = “Dose time delayed”)

The following frequency tables will be produced for each dose level and overall, by SOC and PT in alphabetical order:

- TEAEs leading to temporary discontinuation of at least one trial treatment
- TEAEs leading to temporary discontinuation of all trial treatments
- TEAEs leading to temporary discontinuation of M3814 (regardless of other trial treatments status)
- TEAEs leading to temporary discontinuation of RT (regardless of other trial treatments status)
- TEAEs leading to temporary discontinuation of Cisplatin (regardless of other trial treatments status)
- TEAEs leading to permanent discontinuation of at least one trial treatment
- TEAEs leading to permanent discontinuation of all trial treatments
- TEAEs leading to permanent discontinuation of M3814 (regardless of other trial treatments status)
- TEAEs leading to permanent discontinuation of RT (regardless of other trial treatments status)

- TEAEs leading to permanent discontinuation of Cisplatin (regardless of other trial treatments status)
- TEAEs leading to dose time delayed of RT

15.2.3 Late toxicities

A number of outputs will be produced for late adverse events. An adverse event is defined as late if it starts after the on-treatment period and it meets one of the following criteria:

- It is the first occurrence of adverse event for this participant on MedDRA preferred term level
- It is a recurring adverse event but there is gap between the end date of the previous occurrence and the start date of the re-occurrence (start date of reoccurrence – end date of previous occurrence > 0)
- It is a reccuring adverse event without gap between the end date of the previous occurrence and the start date of the re-occurrence and the grade has worsened:

The following will be produced for late toxicities:

- Table of all late toxicities by worst CTCAE grades: any grade (including AEs with missing grade), grades ≥ 3 , ≥ 4 and 5
- Listing of all late toxicities related to M3814
- Listing of all late toxicities related to radiotherapy
- Listing of all late toxicities grade ≥ 3

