Known and Potential Risks and Benefits to Human Subjects

This clinical trial will be conducted in compliance with the ICH E6 GCP Guidance, and any additional applicable regulatory requirements.

The benefit-risk relationship has been carefully considered in the planning of the trial. Based on the CCI data on M3814 and on published nonclinical and clinical data showing evidence of cell death and tumor shrinkage after single-agent use in tumors with pre-existing altered repair mechanisms, thus illustrating the concept of synthetic lethality, the conduct of this trial is considered justifiable using the dose(s) and dosage regimen(s) of the IMP as specified in this clinical trial protocol [1, 2, 3].

It is known that RT can cause acute toxicities in the form of, for example, radiation dermatitis and mucositis. Definitive concurrent CRT, considered the SoC for inoperable locoregionally advanced SCCHN, is associated with significant acute toxicities including stomatitis (oral mucositis), swallowing dysfunction (odynophagia, dysphagia), decreased appetite, and dermatitis [4, 5, 6, 7]. For incurable head and neck cancers, RT has been demonstrated to be an effective palliative modality and most acute toxicities are generally related to mucosal inflammation and dermatitis, even though the severity and frequency of these AEs were lower compared with CRT in the curative setting [8]. Late toxicities arising 3 months or later after the end of RT can be seen in the form of, for example, xerostomia, esophagitis, pneumonitis, and fibrosis. Patients should be

reminded to contact the trial site immediately in case of toxicities where they will be evaluated and treated as appropriate according to institutional guidelines. Potentially acute and late toxicities can be more severe when RT is given in combination with M3814. This will be evaluated on an ongoing basis for up to 12 months after the end of treatment.

In this trial, the SMC will monitor the benefit-risk ratio on an ongoing basis. The trial will be discontinued in the event of any new findings that indicate a relevant deterioration of the benefit-risk ratio for the subjects, which would render continuation of the trial unjustifiable.

Based on the available **CCI** and clinical data to date, the conduct of the trial specified in this protocol is considered justifiable in subjects with locally advanced disease.

4 Trial Objectives

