Continuous variables will be summarized using descriptive statistics, i.e.

- Number and percentage of subjects (n (%)), number and percentage of subjects with missing values (Missing (%))
- Mean, 95% confidence intervals, as appropriate
- Standard deviation
- Median
- Q1, and Q3
- Minimum, and maximum

If there are no missing values, this should be indicated by a 0 (0.0).

Missing statistics, e.g, when they cannot be calculated, should be presented as “nd”. For example, if n=1, the standard deviation cannot be computed and should be presented as “nd”.

Qualitative variables will be summarized by frequencies and percentages.

Unless otherwise stated, the calculation of proportions will be based on the number of subjects of the analysis set of interest. Therefore, counts of missing observations will be included in the denominator and presented as a separate category.

Presentation of PK Concentration Data

M3814 and **CCI** concentration data will be descriptively summarized using: number of non-missing observations (n), arithmetic mean (Mean), standard deviation (SD), coefficient of variation (CV%), minimum (Min), median (Median) and maximum (Max). In $n \leq 2$, only n, Min, and Max will be reported.

Descriptive statistics of PK concentration data will be calculated using values with the same precision as the source data, and rounded for reporting purposes only. The following conventions will be applied when reporting descriptive statistics of PK concentration data:

Mean, Min, Median, Max: 3 significant digits

SD: 4 significant digits

CV%: 1 decimal place

Presentation of PK Parameter Data

Pharmacokinetic parameter data will be descriptively summarized using: n, Mean, SD, CV%, Min, Median, Max, geometric mean (GeoMean), and the geometric coefficient of variation (GeoCV). For time to reach maximum observed concentration (t_{max}), only n, Min, Median, and Max will be reported.

The PK parameter maximum observed plasma concentration (C_{max}) will be reported with the same precision as the source data. All other PK parameters will be reported to 3 significant figures. In export datasets, as well as in the SDTM PP domain, PK parameters will be provided with full precision, and will not be rounded. Descriptive statistics of PK parameter data will be calculated using full precision values, and rounded for reporting purposes only.

The following conventions will be applied when reporting descriptive statistics of PK parameter data:

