Mean, Min, Median, Max, GeoMean, 95% CI: 3 significant digits

SD: 4 significant digits

CV%, GeoCV%: 1 decimal place

Definition of baseline:

The last measurement prior to first administration of trial treatment (either M3814, RT or Cisplatin) will be used as the baseline measurement.

Definition of treatment day:

Treatment Day 1 is defined as the date of first administration of trial treatment (M3814 and/or RT and/or Cisplatin), the day before is defined as Treatment Day –1 (no Treatment Day 0 is defined).

Definition of on-treatment evaluations for safety analyses:

On-treatment evaluations for safety analyses will be evaluations performed on or after Treatment Day 1 until 30 days after the last dose of trial treatment or the clinical cut-off date (if the treatment is still ongoing).

Definition of duration:

Duration will be calculated by the difference of start and stop date + 1 (e.g. survival time (days) = date of death – date of first dose + 1), if not otherwise specified.

Conversion factors:

The following conversion factors will be used to convert days into months or years:
1 month = 30.4375 days, 1 year = 365.25 days.

Data handling after cut-off date:

Data after cut-off do not undergo the cleaning process. The only exceptions are the date of death and the date last known to be alive. Data obtained after the cut-off will not be displayed in any listings or used for summary statistics (e.g. laboratory values of samples taken after data cut-off, AE with onset date after data cut-off, etc.) will not be included in any analysis or listing.

For any adverse event or concomitant medication starting before the cut-off date, the end date will not be imputed (even if the end date is after the cut-off date) and will be presented as filled in the eCRF at the time of the data export.

Handling of missing data:

For identification of AE treatment emergence, incomplete dates will be handled as follows:

- In case the onset date is completely missing or the onset is in the same year (if the onset year is available only) or the onset is in the same month and year (if the day is missing) as start of trial treatment then the onset date will be replaced by the minimum of start trial treatment and AE resolution date.

- In all other cases, the missing onset day or onset month will be replaced by 1.

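### SAP 15.2.3 starts late toxicity 30 days after last dose where Protocol 3.6 says 3 months or later; it has no summary of persisting toxicity, and its gap rule can count back-to-back records as recurrences

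*SAP*

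**What the plan says.** SAP 15.2.3 gives the start condition: "An adverse event is defined as late if it starts after the on-treatment period and it meets one of the following criteria". SAP 9 ends the on-treatment period for safety as follows: "until 30 days after the last dose of trial treatment or the clinical cut-off date (if the treatment is still ongoing". With the last dose given on the last radiotherapy day, the late window opens at PTD 31. Adverse event reporting closes at PTD 365 (Protocol 7.4.1.3).

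An event starting in that window must then meet one of three criteria:

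1. "It is the first occurrence of adverse event for this participant on MedDRA preferred term level";
2. a recurrence after a gap, defined as "start date of reoccurrence – end date of previous occurrence > 0";
3. a recurrence "without gap between the end date of the previous occurrence and the start date of the re-occurrence and the grade has worsened".

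The outputs are one table of late toxicities by worst grade and three listings (related to M3814, related to radiotherapy, Grade 3 or higher). The section names no analysis population. The SAP 9 default is that, unless otherwise stated, "the calculation of proportions will be based on the number of subjects of the analysis set of interest".

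The protocol uses the word late in more than one way. Section 3.6 writes of "Late toxicities arising 3 months or later after the end of RT". The synopsis and Section 5.1 give the long-term follow-up the purpose of evaluating late signs of radiotherapy toxicity, and the schedules run it from PTD 31 to PTD 365. The synopsis gives the 3-month mid-term follow-up the same purpose; Section 5.1 drops the word late there. The mid-term and long-term visits, and the PTD 270 and 365 visits in Arm A, all evaluate ongoing treatment-emergent events (Protocol 7.1.3.4 to 7.1.3.6).

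**The concern.** Protocol 3.6 says that acute and late toxicity may be more severe when radiotherapy is combined with M3814, and commits to evaluating this for up to 12 months. The table in SAP 15.2.3 is the only planned summary of that evidence. It raises three questions.

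- **Timing.** Are events of the second and third month after radiotherapy shown together with those that Protocol 3.6 would call late, with no way to separate them?
- **Persistence.** Every criterion needs a record with a start date after PTD 30. An in-field toxicity that begins during treatment and is unchanged a year later has no such record.
- **Record splitting.** Can an event that is improving, entered as consecutive records, be counted as a new late toxicity?

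A reader of the table could then misjudge both how much toxicity arose late and how much failed to resolve.

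**Working it through.** The documents state no rate or count for late toxicity, so there is no planned figure to reproduce. The check is day arithmetic plus the three criteria applied to example records.

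**Length of the window.** Inputs: start PTD 31 (SAP 9 and 15.2.3), end PTD 365 (Protocol 7.4.1.3), 1 month = 30.4375 days (SAP 9).
- SAP late window: 365 − 31 + 1 = 335 days.
- Three months: 3 × 30.4375 = 91.3 days.
- Days before that mark: PTD 31 to 90 = 60 days; 60 / 335 = 17.9%.
- Days left from PTD 91: 335 − 60 = 275.

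With deaths and losses, the early part takes a larger share of person-time. The documents give no survival figure, so this is an assumption: exponential attrition from PTD 30 with median m months and λ = ln 2 / (30.4375 m). The share is (1 − e^(−60λ)) / (1 − e^(−335λ)): 20% at m = 24, 23% at 12, 28% at 6 and 40% at 3.

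**Overlap with the DLT window.** Protocol 5.1.1 says this window serves the evaluation of acute toxicity.
- Arm B: Table 5 runs it to PTD 35. By calendar, 33 to 35 fractions at 5 per week end on day 45 to 49, and 12 weeks is 84 days, so the window closes at PTD 35 to 39 (84 − 49 and 84 − 45). An event starting on PTD 31 to 35 can be both a DLT and a late toxicity. With the maximum 7-day delay the calendar close moves to PTD 28 to 32, and the overlap shrinks or disappears.
- Arm A: 10 fractions end on day 12 to 14 and 5 weeks is 35 days, so the window closes at PTD 21 to 23. There is no overlap.

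**Criteria applied to records of one preferred term.**

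| Record history | Late under 15.2.3? |
|---|---|
| First onset PTD 35 | Yes |
| First onset PTD 120 | Yes |
| Grade 3 from PTD 20, one record open to PTD 365 | No |
| Grade 3 to Grade 3, ends and restarts PTD 60 (difference 0) | No |
| Grade 3 to Grade 2, ends and restarts PTD 60 (difference 0) | No |
| Grade 2 to Grade 3, ends and restarts PTD 60 (difference 0) | Yes |
| Grade 3 to Grade 2, ends PTD 60, restarts PTD 61 (difference 1) | Yes |

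The last row is the gap problem. SAP 9 counts durations inclusively (stop − start + 1), so a record ending on day d and another starting on d + 1 leave no uncovered day. Their difference is 1, which exceeds 0, so they pass criterion 2 at any grade and the worsening test in criterion 3 is bypassed. Split records are foreseen in the SAP: Section 15.2 describes a pre-treatment event followed directly by the same term at lower grade and does not count it as treatment-emergent. In 15.2.3 the equivalent protection works only when the two dates are identical.

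**The case against.** Protocol 3.6 is a risk narrative, not an analysis definition. The operational text, with long-term follow-up for late signs from PTD 31, matches the SAP cut, and that cut leaves no hole after the treatment-emergent period. This stands. A reader might infer that the SAP contradicts the protocol; the documents support only that two starting points coexist and the table does not distinguish them.

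A reader might also infer that the table takes any event after 30 days, or that it misses chronic damage. Neither holds. Gap-free recurrences that do not worsen are excluded, while new onset after PTD 30 and gap-free worsening are included. Persisting events are not lost either: the all-event listing (SAP 15.2.1) carries start and end dates, grade and outcome. In Arm B, related Grade 3 dysphagia lasting beyond 4 weeks after treatment would ordinarily meet the DLT definition inside the 12-week window, subject to confirmation by the Safety Monitoring Committee, which may also name late in-field toxicities as DLTs at any time (Protocol 7.4.1.5). In Arm A that route is less sure: the 4-week allowance for mucositis, stomatitis-associated toxicity and dermatitis runs to PTD 28, past the end of the DLT window. What survives is a missing summary, not missing data.

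The gap problem depends on how sites date consecutive records, which the documents do not show. Criterion 3 may presuppose same-day splits. That limits the claim to a rule that can misclassify.

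On the denominator, 15.2.3 states no population, and the use of all treated subjects is inferred from a default. The documents give no survival or late-event figures, so they do not support any stated bias in the percentages.

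**Conclusion.** Three limited defects stand in a descriptive secondary output.

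- The documents hold two starting points for late toxicity. They differ by 60 of 335 window days (17.9%, or 20% to 40% of person-time for assumed medians of 24 down to 3 months). In Arm B, PTD 31 to 35 also falls within the DLT window if radiotherapy is not delayed.
- Toxicity that starts on treatment and persists without worsening is absent from the late table, and no summary anywhere shows persistence.
- If sites date a split record one day after the previous end date, an improving or unchanged event counts as a new late toxicity.

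The day counts assume that the last dose falls on the last radiotherapy day and that follow-up reaches PTD 365. The number of events affected cannot be computed. Sample size, the planned DLT analysis and error rates are untouched. The SAP should be changed because potentiated late toxicity is a named risk of the combination and this is its only planned summary.

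**What to change.** In SAP 15.2.3:

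- **(a)** Keep the PTD 31 start, but split the table into onset before 3 months and onset at 3 months or later after the end of radiotherapy. This serves both protocol descriptions. Add a note that Arm B events on PTD 31 to 35 may also be DLTs.
- **(b)** Add a summary of treatment-emergent events still ongoing at about 3, 6 and 12 months after radiotherapy, by grade of the record open at that time, among subjects still in follow-up then. Derive it from event start and end dates. If grade changes are not entered as separate records, footnote that the grade shown is the one recorded for the whole event.
- **(c)** Change the gap criterion to more than 1 day and apply criterion 3 to differences of 0 or 1. Under a same-day convention this loses nothing of substance; under a next-day convention it removes the misclassification.
- **(d)** Show the number of subjects alive and in follow-up at the start of each window beside the counts.

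The cost is a wording change, a few extra descriptive rows and one table. No new data are needed.

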Following completion of the screening and baseline evaluations, subjects enrolled in the ancillary cPoP part of the trial will receive a single high dose of RT (10-25 Gy) on Lesion 1 on Day 1 and on Lesion 2 on Day 2. A single dose of the capsule formulation of M3814 will be administered on Day 2, 1.5 hours (\pm 30 minutes) before the start of RT (see Section 6.3.2 for details on dosing). Three fixed dose levels are planned (100 mg, 200 mg, and 400 mg) (see Table 12 for details).

The ancillary cPoP part of the trial will initially be conducted with the capsule; however, additional cohorts of M3814 (CC1 formulation) may be introduced. The starting dose and subsequent dose levels of M3814 (CC1 formulation) will be defined by the SMC based on PK and safety data generated in ongoing clinical studies evaluating the safety, tolerability, PK, and PD of M3814 (CC1 formulation).

It is planned to enroll 11 subjects with (sub)cutaneous tumor/metastases in the ancillary cPoP part of the trial using M3814 capsule formulation and approximately 12 additional subjects with (sub)cutaneous tumor/metastases using M3814 [CC1] formulation.

Follow-up Periods

Phase Ia/Ib

The follow-up period for all subjects in the Phase Ia and Ib parts of the trial will consist of the following:

- DLT Period: A 5-week (Arm A) or 12-week (Arm B) DLT period after the first dose of M3814 for the evaluation of 'acute' systemic and local toxicity in all subjects in Phase Ia and a 12-week DLT period after the first dose of M3814 in the first 3 subjects of the safety run-in part in the NSCLC expansion cohort during Phase Ib (Arm A)
- Short-term Safety Follow-up: A follow-up for a period of 30 days after the end of RT for evaluation of safety
- Mid-term Safety Follow-up: A safety follow-up period of 3 months after end of RT to evaluate signs of RT-induced toxicity on normal surrounding tissues
- Long-term Safety Follow-up: A safety follow-up period until 12 months after end of RT to evaluate late signs of RT-induced toxicity on normal surrounding tissues
- Survival Follow-up: A follow-up period that will continue until 12 months after the last subject has stopped RT/CRT.

Ancillary cPoP part

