6.6.2 Prohibited Medicines

As stated in Section [5.3.2](#), subjects must not have received chemotherapy, immunotherapy, hormonal therapy, biologic therapy, or any other anticancer therapy or any investigational agent

within 28 days of the first dose of IMP administration (6 weeks for nitrosoureas or mitomycin C), except for subjects with rapidly growing tumors localized in the head and neck region or thorax where the treating physician cannot wait for 28 days. These therapies are also prohibited during the treatment period and up to 30 days after RT, with the exception of concurrent cisplatin in the SCCHN population (Arm B). During the treatment period and up to 30 days after RT, any other investigational agent, chemotherapy, extensive RT (involving $\geq 30\%$ of bone marrow) or any other anticancer therapy (biologics or other targeted therapy) and antineoplastic steroid therapy are also prohibited (Phase Ia and Phase Ib only). Use of any investigational agent during the entire trial duration is not permitted.

Medications or herbal supplements known to be potent inhibitors or inducers of CYP3A or CYP2C19, or drugs mainly metabolized by CYP3A with a narrow therapeutic index as judged by the Investigator (and after optional consultation with the Sponsor) are prohibited (see Section 6.6.4 for details).

The solubility of M3814 is pH dependent; therefore, antacid drugs, H₂-blocker and PPIs might affect absorption. H₂-blockers or PPIs should be stopped 5 days prior to the first treatment, and avoided during the entire treatment period with IMP. Antacid drugs should not be taken 1 hour before IMP administration until 2 hours after IMP administration.

If the administration of a nonpermitted concomitant drug becomes necessary during the treatment period, e.g., due to AEs, the subject should be discontinued from the trial treatment and complete all assessments listed under the ETT visit.

See also Section 6.6.4 for details of possible drug-drug interactions with and by concomitant medication.

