12.5 Anti-cancer post-treatment

Anti-cancer post-treatments will be listed according to eCRF page “Anti-cancer treatment after discontinuation”. The listing will include: subject identification number, formulation, dose level and all corresponding collected data-fields on the corresponding eCRF page.

Anti-cancer post-surgeries and post-radiotherapies will also be listed according to eCRF pages “Anti-cancer surgeries after discontinuation” and “Anti-cancer radiotherapy after discontinuation”.

13 Treatment Compliance and Exposure

Population: SAF Analysis Set

Treatment compliance and exposure will be listed and summarized by dose level and overall using SAF Analysis set.

All dosing calculations and summaries will be based on “MSC2490484A Administration”, “Radiotherapy Administration” and “Cisplatin Administration” eCRF pages.

In Phase Ia, subjects will receive treatment with M3814 at a starting dose of 100 mg QD for Arm A and 50 mg QD for Arm B, which will be given 1.5 hours before each RT fraction (3 Gy) for up to 10 fractions (Arm A) or 2 Gy for 33 to 35 fractions (Arm B). In addition, in Arm B, on Fraction Days 1 and 31 for the 100 mg/m² dose, or weekly for the 40 mg/m² dose, cisplatin will be given after oral intake of M3814 and before RT is started. Dose escalation will continue up to a maximum dose of M3814 800 mg/day.

Number of treatment administrations

The number of fraction days of treatment will be summarized for Radiotherapy by dose level and overall.

CONFIDENTIAL
INFORMATION

24/60

The number of days of treatment will be summarized for M3814 by dose level and overall.

The number of infusions of Cisplatin will be summarized for both treatment schedules: 100 mg/m² twice (FD1, FD31) or 40 mg/m² weekly.

Cumulative dose

The cumulative dose (mg) of M3814 will be calculated as the sum of the total daily doses that the subject received.

The cumulative dose (Gy) of RT will be calculated as the sum of the total daily doses that the subject received.

The cumulative dose (mg/m²) of cisplatin per subject is the sum of the total dose that the subject received at each visit. At a given visit, the total dose (mg/m²) received is derived as:

$$\text{Total dose} = \text{Total dose administered (mg)} / \text{recalculated BSA (m}^2\text{)}$$

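### The only late-toxicity table is all-cause with no split at new anticancer therapy, so its rates can mix toxicity of later treatment with late RT/M3814 toxicity

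*SAP*

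**What the plan says.** SAP 15.2.3 sets the definition: "An adverse event is defined as late if it starts after the on-treatment period and it meets one of the following criteria". The three criteria are a first occurrence of the preferred term, a recurrence after a gap, and a gap-free recurrence at a worse grade. None refers to causality or to later therapy.

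Four outputs follow:

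- one table, "Table of all late toxicities by worst CTCAE grades";
- "Listing of all late toxicities related to M3814";
- "Listing of all late toxicities related to radiotherapy";
- a listing of late events of Grade 3 or higher, whatever the cause.

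No late listing is planned for cisplatin. SAP 15.2.3 names no layout, so the table falls under the section 9 default: by arm, formulation, dose level and overall.

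The long-term follow-up is described in Protocol 5.1 as "A safety follow-up period until 12 months after end of RT to evaluate late signs of RT-induced toxicity on normal surrounding tissues". On other anticancer treatment, Protocol 6.6.2 says: "These therapies are also prohibited during the treatment period and up to 30 days after RT", with cisplatin in Arm B excepted. What subjects receive afterwards is handled in SAP 12.5: "Anti-cancer post-treatments will be listed according to eCRF page". Later surgery and radiotherapy are listed there too. Nothing connects these listings to the late-toxicity outputs.

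**The concern.** The follow-up is meant to show late radiation damage and whether M3814 makes it worse. Protocol 3.6 warns that late toxicities may be more severe with the combination. A reader of the report will look to the late-toxicity table for that signal.

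As planned, the table counts a cytopenia or neuropathy caused by a later regimen in the same way as a late in-field injury. Rates by dose level would then depend partly on how many subjects at each level went on to other treatment. SAP section 4 says these analyses go into the clinical trial report and into regulatory submissions or future manuscripts, so the mixed rate could be read as a property of the M3814 dose.

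**Working it through.** The plan states no late-toxicity figure, so there is none to reproduce. The check compares the passages and then illustrates the mechanism on assumed inputs.

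**1. Do the windows overlap?**

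- SAP section 9 ends the on-treatment period 30 days after the last dose of trial treatment (M3814, RT or cisplatin).
- Protocol 6.6.2 ends the ban on other anticancer therapy 30 days after RT.
- Protocol 7.4.1.3 ends AE reporting at post-treatment day (PTD) 365.

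M3814 is given on RT days, so the first two normally end together. Counting from the end of RT, the late window is days 31 to 365, or 365 − 30 = 335 days, and other non-investigational anticancer therapy is allowed on all 335. No rule censors or splits AEs when it starts.

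**2. What does the SAP do for TEAEs?** SAP 15.2.1 gives worst-grade tables for all TEAEs and for those related to any trial treatment, M3814, RT and cisplatin. Late events get only the first kind of table. The all-AE listing carries a flag for onset after the start of the COVID-19 pandemic, but none for onset after new anticancer therapy.

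**3. Will new late events be recorded?** The protocol gives two answers.

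- Protocol 7.4.1.3 and 7.4.1.7 have AEs reported and assessed continuously to PTD 365.
- The schedule footnotes to Tables 1 to 6 and Protocol 7.1.3.4 to 7.1.3.6 limit AE work at the later visits to TEAEs that are still ongoing. The PTD 210 and 312 contacts are phone calls about long-term RT toxicity.

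Under 7.4.1.3 a TEAE starts no later than day 30 after RT. Read literally, the second set of passages leaves out events that first appear in the late window, which are most of what SAP 15.2.3 sets out to count.

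**4. Hypothetical size.** None of these inputs is in the documents. Let p be a subject's chance of a Grade ≥3 late event from trial treatment, f the share starting new therapy, and q the chance of a Grade ≥3 event on that therapy. Assuming independence and full one-year follow-up:

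table rate = 1 − (1 − p)(1 − f·q); inflation = (1 − p)·f·q

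| p | f | q | Table rate |
|---|---|---|---|
| 10% | 0.3 | 0.2 | 1 − 0.90 × 0.94 = 15.4% |
| 10% | 0.3 | 0.4 | 1 − 0.90 × 0.88 = 20.8% |
| 10% | 0.7 | 0.4 | 1 − 0.90 × 0.72 = 35.2% |

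For p of 5–20%, f of 30–70% and q of 20–40%, the inflation runs from 0.80 × 0.06 = 4.8 points to 0.95 × 0.28 = 26.6 points. The second and third rows show two dose levels with the same true rate differing by 14.4 points only because uptake of later therapy differs.

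The chance of at least one such subject at a dose level is 1 − (1 − f·q)ⁿ. For f·q from 0.06 to 0.28 this is 17–63% with n = 3 and 31–86% with n = 6.

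**The case against.** Attribution is not absent. Late events related to M3814, those related to RT, and all of Grade ≥3 are listed by subject. With cohorts of 3, up to 6 per tablet dose level, and cohorts at one dose pooled, a reader can count cases by hand. The listing of all AEs also covers events that are not treatment-emergent. All-cause reporting is a defensible, conservative choice in open-label dose escalation, and a related-event table would rest on the same investigator judgement as the listings. These points stand. They make this an improvement in reporting rather than a loss of information, but listings give no rate by grade and dose level.

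Three stronger readings are tempting and are not supported:

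- *Every adverse event after treatment is counted.* Gap-free recurrence without worsening is excluded, and Protocol 7.4.1.1 generally does not count disease progression as an AE.
- *The rates will be inflated by a known or large amount.* Nothing gives the uptake or toxicity of later therapy. Protocol 6.6.2 bars investigational agents for the whole trial, Protocol 5.5.2 requires withdrawal on joining another trial, and Arm A eligibility allows a life expectancy of only 3 months. If sites follow the footnotes, new late events are under-collected, which would reduce the inflation.
- *Dose selection is biased.* SMC analyses have a separate plan (SAP section 4), and the SMC may itself classify in-field late radiation toxicity as a DLT (Protocol 7.4.1.5). No stated dose rule uses this table.

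**Conclusion.** The point holds as one about reporting and interpreting late safety. The only tabulated late rates are all-cause, they cover a window that opens at about the time other anticancer therapy becomes allowed, and nothing separates events starting after such therapy. Attributed late events are available only as listings, with none for cisplatin in Arm B.

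The direction is clear: recorded events caused by later therapy can only add to the table. The amount is not known. The figures in the working show the mechanism and are not estimates for this trial. The conclusion rests on two assumptions: that some subjects start non-investigational anticancer therapy within the year, and that new late AEs are recorded after that. The second is uncertain until the conflicting protocol passages are reconciled.

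**What to change.** 1. Keep the all-cause table.
2. Add a table of late toxicities related to trial treatment (M3814, RT or, in Arm B, cisplatin) by worst grade and dose level. Count missing causality as related, as SAP 15.2 does for trial treatment.
3. Flag or split late events that start on or after the first new anticancer therapy, using the dates behind SAP 12.5 (drug, surgery and radiotherapy pages).
4. Add a listing of cisplatin-related late toxicities for Arm B. The SAP 15.2 bullet that defines cisplatin-related events names M3814 as the related treatment and should be corrected first.
5. Reconcile Protocol 7.4.1.3 and 7.4.1.7 with the schedule footnotes and 7.1.3.4 to 7.1.3.6 on which AEs are recorded after day 30, and state in the report which practice sites followed.

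Items 2 to 4 cost one table, one flag and one short listing. They need no new data collection: Protocol 7.4.1.2 requires causality for each AE, and 7.1.3.5 requires the date and regimen of new treatment in the eCRF. The drawback is reliance on open-label investigator causality, which is why the all-cause table stays beside the new one.
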